4.2 Rationale of key elements of the study design

Current guidelines advocate the use of ACE-inhibitors (or angiotensin receptor blockers if ACE-inhibitor contraindicated/not tolerated) along with beta-blockers and mineralocorticoid receptor antagonists to reduce morbidity and mortality after myocardial infarction.²⁵ The role of ACE-inhibitors/ARBs in preventing adverse remodelling after myocardial infarction is well established. A meta-analysis of 16 trials examining ACE-inhibition after myocardial infarction demonstrated a significant improvement in reduction of left ventricular volumes at both short and long-term follow up in patients with reduced left ventricular ejection who were administered an ACE-inhibitor.²⁸ Similarly, in patients with asymptomatic LVSD, usually as a result of remote myocardial infarction, ACE inhibitor therapy attenuates the progressive left ventricular remodelling.²⁹

To date, the administration of an ARNI has not been studied in patients after myocardial infarction. Sacubitril/valsartan (brand name “Entresto”) is a first-in-class ARNI, which has been studied in a pivotal trial in the setting of chronic HF-REF in patients with LV ejection fractions of $\leq 40\%$.²⁴ Sacubitril/valsartan (at a target dose of 97mg/103mg BD) when compared to the gold standard ACE-inhibitor, enalapril (target dose 10mg BD), was associated with a significant reduction in cardiovascular death and hospitalisation for heart failure. Recently, sacubitril/valsartan was shown to have favourable effects on left ventricular remodelling in an experimental rat model of acute myocardial infarction, although in this study sacubitril/valsartan was compared to control rather than an ARB.²⁶

The target dose (97mg/103mg BD) of sacubitril/valsartan is based on the clinical benefit and safety results seen with this dose in PARADIGM-HF.²⁴ In this trial there was a high prevalence of ischaemic cardiomyopathy (60%), with 43% of patients having had a prior MI. This target dose delivers equivalent valsartan exposure (assessed by AUC) as valsartan 160mg BD and biomarker analysis (increase in ANP and cGMP) indicates that this dose delivers approximately 90% of its maximal NEP inhibition.³⁰ The target dose of valsartan (160mg BD) was shown to be as effective as the ACE inhibitor captopril (target dose 50mg three times daily) in the VALIANT trial at reducing mortality, recurrent myocardial infarction and hospitalisation for heart failure in patients with LVSD and/or HF post MI.⁹

CMR is the gold standard means of assessment of LV mass, volumes and ejection fraction. It has the additional benefit of allowing assessment of myocardial viability, myocardial fibrosis and regional dysfunction.³¹ LVESVI has been shown to be a major determinant of survival after myocardial infarction.^{32,33} The degree of LV remodelling and effect of treatment will be measured by the primary endpoint of the change in LVESVI from baseline to 12 (+/- 3months) months.

5 Patient Population

This study will recruit male and female patients aged ≥ 18 years with asymptomatic left ventricular systolic dysfunction (i.e. no evidence of clinical and/or radiological heart failure) > 3 months post acute myocardial infarction.

Patients will be required to satisfy the following criteria. Eligibility waivers to the inclusion / exclusion criteria are NOT permitted.

5.1 Inclusion Criteria

- Acute myocardial infarction at least 3 months prior to recruitment
- LVEF ≤ 40% as measured by transthoracic echocardiography
- Ability to provide written, informed consent
- Age ≥18 years
- Tolerance of a minimum dose of ACE inhibitor/ARB (ramipril 2.5mg BD or equivalent)
- Treatment with a beta-blocker unless not tolerated or contraindicated

5.2 Exclusion Criteria

- Contraindication to CMR (ferrous prosthesis, implantable cardiac device or severe claustrophobia)
- Clinical and/or radiological heart failure (NYHA≥2)
- Symptomatic hypotension and/or systolic blood pressure <100mmHg
- eGFR < 30 mL/min/1.73m² and/or serum potassium >5.2mmol/L
- Persistent/permanent atrial fibrillation
- History of AMI within last 3 months
- History of hypersensitivity or allergy to ACE-inhibitors/ARB
- History of angioedema
- Known hypersensitivity to the active study drug substances, contrast media or any of the excipients
- Obesity (where body girth exceeds MRI scanner diameter)
- Pregnancy, planning pregnancy, or breast feeding
- Inability to give informed consent or comply with study protocol
- Evidence of hepatic disease as determined by any one of the following: AST or ALT values exceeding 2 x ULN at Visit 1, history of hepatic encephalopathy, history of oesophageal varices, or history of portacaval shunt
- History of biliary cirrhosis and cholestasis
- Active treatment with cholestyramine or colestipol resins
- Active treatment with lithium or direct renin inhibitor
- Participation in another intervention study involving a drug or device within the past 90 days (co-enrolment in observational studies is permitted)

5.3 Women of child bearing potential

Women of childbearing potential must be currently adhering to, or be willing to use, highly effective birth control methods for study treatment duration and for seven days thereafter including:

- Combined hormonal contraception (oestrogen and progestogen containing medication) either orally, intravaginally, or transdermally
- Progesterone only hormonal contraception either orally, injected, or implanted
- Progesterone only hormonal contraception either orally, injected, or implanted

- Intrauterine device (IUD)
- Intrauterine hormone release system (IUS)
- Bilateral fallopian tube occlusion
- Vasectomised partner
- Complete sexual abstinence where this is their preferred and usual lifestyle

Women of child bearing potential (WOCBP) comprises women who have experienced menarche and who have not undergone successful surgical sterilisation (hysterectomy, bilateral tubal ligation, or bilateral oophorectomy) or who are not post-menopausal defined as:

- Women who have had amenorrhea for \geq 12 consecutive months (without another medical cause) and who have a documented serum follicle-stimulating hormone (FSH) level $>$ 35 mIU/mL.
- Women who have irregular menstrual periods and a documented serum FSH level $>$ 35 mIU/mL.
- Females of childbearing potential must have a negative pregnancy test within 7 days prior to the initiation of treatment.

Pregnancy tests will be performed in WOBCP at the following visits: Visit 1 (week 0), 4 (week 4), 6 (week 14), 7 (week 26), 8 (Week 39), and 9 (week 52). Should this test be positive, then the patient will be immediately withdrawn from the trial and study drug will be discontinued.

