5.5 Pregnancy

The Investigator must ensure that all patients are aware at the start of a clinical trial of the importance of reporting all pregnancies (in themselves and their partners) that occur whilst being treated with IMP and occurring up to 1 month after the last IMP administration. The Investigator should offer counselling to the patient and/or the partner, and discuss the risks of continuing with the pregnancy and the possible effects on the foetus. Monitoring of the patient and the baby should continue until the conclusion of the pregnancy, if the patient or patient's partner has consented to this. See section 10.7 for information on pharmacovigilance reporting requirements.

6 Study Treatment

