In women of child-bearing potential, a possible risk of developmental toxicity cannot be excluded. Women of child-bearing potential should therefore use a highly effective method of contraception during study participation. If there is any question that the patient will not reliably comply, they should not be entered in the study. Pregnancy testing will be performed prior to randomisation and at regular intervals during the study in women of child-bearing potential.

8 Visit schedule and assessments

Table 9-1 details all of the visits and indicates with an “x” when study assessments or procedures are performed. Patients should be seen for all visits at the designated time or as close to as possible. These visits windows are what investigators should endeavor to stick to and wherever possible should be met. Any visits out with these timeframes will not be considered protocol violations but will be dealt with in the statistical analysis plan.

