8.5 Definition of end of trial

The end of the trial is defined as the date of the last patient's 52-week (+/- 3 months) study visit plus additional 30 days of event reporting.

9 Assessment, samples and data collection

Trial data will be recorded on trial-specific eCRFs. Only the patient's unique identifier number, date of birth and initials will be recorded on the eCRF in order to identify the patient. Any missing or discrepant data queries will be sent to appropriate research

team member(s) to be reviewed. Biochemical samples will be stored in the QUEH Biochemistry department and the BHF Glasgow Cardiovascular Research Centre to be analysed in batches on completion of the trial. Analysis of echocardiograms and CMR imaging will be performed offline.

Table 9-1 Schedule of Assessments

Study Procedure	Screening (>3months post myocardial infarction)	Visit 1 - Randomisation (Week 0)	Visit 2 (Week 1 ± 3 days)	Visit 3 (Week 2± 3 days)	Visit 4 (Week 4± 3 days)	Visit 5 (Week 5± 3 days)	Visit 6 (Week 14 ± 7 days)	Visit 7 (Week 26 ± 7 days)	Visit 8 (Week 39 ± 7 days)	Visit 9 (Week 52 ± 3 months)
Review Inclusion/Exclusion Criteria	X									
Echocardiogram	X									
Obtain informed consent	X	X								
Cardiac MRI		X								X
Physical examination		X	X		X			X		X
Medical history	X	X								
Concomitant medications	X	X	X	X	X	X	X	X	X	X
Vital Signs (Blood pressure/Heart rate)	X	X	X	X	X	X	X	X	X	X
12 Lead ECG		X								
Spot urine collection		X						X		X
Venepuncture (Urea and Electrolytes/FBC and LFTs)	X&	X	X	X	X	X	X	X	X	X
Venepuncture (Biochemical/hormonal/biomarker analysis)		X						X		X
Pregnancy testing in WoCBP		X			X		X	X	X	X
Patient global assessment questionnaire								X		X
IMP Dispensing*		X			X		X	X		
Up-titrate IMP#					X					
IMP Administration+		X	X	X	X	X	X	X	X	X
Adverse event reporting			X	X	X	X	X	X	X	X
Study completion										X

* Study drug will be introduced at equivalent dose to existing ACE-i/ARB treatment (Dose level 2 or 3) at investigator's discretion

#Up-titration not required if patient already on dose level 3 but down titration to dose level 2 permitted in response to COVID-19

&If not done in the preceding 6 months

+Emergency IMP dispensing permitted during COVID-19 pandemic

10 Pharmacovigilance

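### Protocol section 5.3 counts women who still have irregular periods as post-menopausal on one FSH value, which on the intended reading removes the contraception and pregnancy-test rules

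*Protocol*

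**What the plan says.** Protocol section 5.3 describes WOCBP as women past menarche who have not been surgically sterilised, "or who are not post-menopausal defined as" in a bulleted list.

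- The first bullet requires amenorrhoea of at least 12 "consecutive months (without another medical cause) and who have a documented serum follicle-stimulating hormone (FSH) level" above 35 mIU/mL.
- The second bullet reads "Women who have irregular menstrual periods and a documented serum FSH level" above 35 mIU/mL, and sets no further condition.
- The third bullet is not part of a definition of menopause at all: "Females of childbearing potential must have a negative pregnancy test within 7 days prior to the initiation of treatment".

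The protective rules are written for WOCBP only. Section 5.3 requires highly effective contraception for the treatment period and seven days after it, and lists tests at Visits 1, 4, 6, 7, 8 and 9. Section 7 repeats the contraception rule: "Women of child-bearing potential should therefore use a highly effective method of contraception during study participation". The row in Table 9-1 is headed "Pregnancy testing in WoCBP".

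Three provisions cover every woman: the exclusion in section 5.2 ("Pregnancy, planning pregnancy, or breast feeding"), the duty in section 5.5 to make all patients aware of "the importance of reporting all pregnancies (in themselves and their partners"), and permanent discontinuation of study drug on pregnancy in section 6.5.

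**The concern.** The two routes use the same FSH threshold but not the same standard. For a woman who has stopped bleeding, the protocol does not accept FSH above 35 mIU/mL alone; it also wants 12 months of amenorrhoea with no other medical cause. For a woman who still bleeds irregularly, one documented value is enough. The weaker evidence of menopause thus meets the lower bar.

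What is at stake is participant and foetal safety, not inference. A woman classed as post-menopausal by the second bullet loses every rule that would prevent a pregnancy or detect one by test, in a trial whose own risk section does not exclude developmental toxicity. The provisions that still cover her depend on a pregnancy being noticed, and a missed period is a poor signal in someone whose periods are irregular.

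**Working it through.** There is no planned figure to reproduce. The check is of logic and schedule.

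**1. The two routes compared (section 5.3)**

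| | Bullet 1 | Bullet 2 |
|---|---|---|
| FSH above 35 mIU/mL | required | required |
| Amenorrhoea of at least 12 months | required | not required |
| Other medical cause excluded | required | not required |
| Repeat FSH or age limit | not required | not required |

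Bullet 2 therefore bypasses the 12-month condition for women with irregular periods.

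**2. The lead-in sentence.** For women past menarche, let S = sterilised and PM = post-menopausal.

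| S | PM | Literal: not S **or** not PM | Intended: not S **and** not PM |
|---|---|---|---|
| no | no | WOCBP | WOCBP |
| no | yes | WOCBP | not WOCBP |
| yes | no | WOCBP | not WOCBP |
| yes | yes | not WOCBP | not WOCBP |

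The rules differ in 2 of 4 combinations. Under the literal rule every unsterilised woman is WOCBP even if truly post-menopausal, so the exemption never operates for her, and a woman after hysterectomy who is not post-menopausal is WOCBP too. Only the intended rule gives the exemption any effect for unsterilised women. Under it, a woman who meets bullet 2 falls in the second row and is not WOCBP.

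**3. What she loses**

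- Scheduled tests at weeks 0, 4, 14, 26, 39 and 52: six for a WOCBP, none for her.
- The negative test in the 7 days before treatment: not required.
- Contraception: not required during treatment or for the 7 days after it.

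**4. For how long.** Treatment lasts 12 months ± 3 months, that is 9 to 15 months. Taking 3 months as 13 weeks, Visit 9 falls between 52 − 13 = 39 and 52 + 13 = 65 weeks. She has no scheduled test in that whole time.

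For comparison, the gaps between a WOCBP's scheduled tests are 4 − 0 = 4, 14 − 4 = 10, 26 − 14 = 12, 39 − 26 = 13 and 52 − 39 = 13 weeks. The last can reach 65 − 39 = 26 weeks if Visit 9 is 3 months late.

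Section 6.1 also allows COVID-19 resupply until the final MRI, up to 18 months, so 15 months may not be the upper limit for every participant.

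**5. How many women.** The documents give no sex or age distribution. Table 9-1 has no FSH row, so bullet 2 operates only where a value happens to be on record; a woman without one stays WOCBP. SAP section 2.3 does list FSH level among the baseline summaries, so some values are expected. The number affected cannot be computed; few of 100, or none, is a judgement.

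**The case against.** The strongest reply is that the harm depends on a reading the text does not state. As written, the or keeps an unsterilised woman with irregular periods in WOCBP, with all the protections, so the literal text errs on the safe side. That is correct, and the gap is conditional on the intended reading. It does not rescue the section, because the literal reading defeats the post-menopausal exemption. It does carry a practical warning: correcting the or without deleting bullet 2 would turn a conditional gap into a definite one.

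The documents also give no probability of pregnancy for women with irregular periods and raised FSH, so calling bullet 2 inadequate might seem to need outside clinical standards. The point made here is narrower: the protocol's own first bullet does not accept that FSH level as sufficient. A repeat FSH or an age limit could be proposed instead of deletion, but the documents offer no basis for choosing either.

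It is fair, too, that participants must already tolerate an ACE inhibitor or ARB and the comparator is an ARB, so part of the exposure precedes the trial. Sacubitril is new to them, however, and the protocol sets its contraception and testing rules despite that background treatment.

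Finally, very few women, perhaps none, are involved, and the pregnancy exclusion, reporting advice, discontinuation rule and pregnancy reporting to the sponsor (section 10.7) remain. All of this stands and limits the weight of the point. None of those provisions requires a test or contraception.

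**Conclusion.** The concern holds. On the only reading that gives the post-menopausal exemption any effect for unsterilised women, section 5.3 exempts a woman who still menstruates irregularly on one FSH value that the same section treats as insufficient without 12 months of amenorrhoea. Nothing elsewhere in the protocol brings her back under the WOCBP rules. Per affected woman the loss is six of six scheduled tests, the pre-treatment test, and the contraception requirement for 9 to 15 months plus 7 days.

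This rests on two assumptions: that investigators apply the intended rather than the literal definition, and that at least one woman with irregular periods has a documented FSH above 35 mIU/mL. The number affected is unknown and probably very small. Sample size, power and the primary analysis are unaffected. It should be corrected as a safety point in the eligibility text.

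**What to change.** Amend section 5.3 as one package:

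1. Delete the second bullet. Women with irregular periods then remain WOCBP whatever their FSH, and 12 months of amenorrhoea with raised FSH is the only post-menopausal route.
2. Reword the lead-in so that a WOCBP has reached menarche, has not been surgically sterilised **and** is not post-menopausal. Do not make this change without the first.
3. Move the sentence on the negative test in the 7 days before treatment out of the definition list, to stand with the testing schedule.

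As an editorial matter only, tubal ligation or occlusion appears both as sterilisation and as a contraceptive method; state one classification.

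If participants have already been enrolled, use the baseline WOCBP status and FSH data to check whether anyone was exempted under the second bullet, and reclassify any such woman still on treatment.

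The cost is a wording change made through a protocol amendment. Any affected woman would have to accept the contraception rule and up to six pregnancy tests, all at visits she already attends.

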5.4 Males whose partner could become pregnant

To be eligible for this study participants will be taking an ACEI or ARB. These are similar to the study medicines and with the information currently available there is no indication that men should avoid fathering a child whilst taking the study medicines. Males whose partner may have become pregnant during the study must be advised to inform the investigator immediately. If the partner consents data may be collected about the pregnancy and the health of the partner and their baby.

5.5 Pregnancy

The Investigator must ensure that all patients are aware at the start of a clinical trial of the importance of reporting all pregnancies (in themselves and their partners) that occur whilst being treated with IMP and occurring up to 1 month after the last IMP administration. The Investigator should offer counselling to the patient and/or the partner, and discuss the risks of continuing with the pregnancy and the possible effects on the foetus. Monitoring of the patient and the baby should continue until the conclusion of the pregnancy, if the patient or patient's partner has consented to this. See section 10.7 for information on pharmacovigilance reporting requirements.

6 Study Treatment

6.1 Investigational and control drugs

All eligible patients will be randomised 1:1 to either sacubitril/valsartan titrated to a target dose of 97mg/103mg B.D. or valsartan titrated to a target dose of 160mg BD in a double blinded manner for the duration of the study. Patients will continue on optimal standard of care background therapy to treat their index MI and any co-morbid conditions in accordance with local guidelines with the exception of an ACE inhibitor or ARB as this will be replaced by study drug. In order to minimise the potential risk of angioedema due to overlapping ACE and NEP inhibition all patients prescribed an ACE inhibitor pre-randomisation will undergo a 36-hour “washout” period following randomisation prior to first dose of study drug. The use of open label ACE inhibitor or ARB in addition to the randomised study drug is strictly prohibited for the duration of the trial.

In order for adequate blinding of treatment allocation, patients will be required to take a total of two tablets (one tablet from the sacubitril/valsartan or sacubitril/valsartan matching placebo pack and one tablet from the valsartan or valsartan matching placebo pack) twice a day for the duration of the study.

The following study drugs will be provided:

- Sacubitril/valsartan 24mg/26mg, 49mg/51mg and 97mg/103mg tablets and matching placebo.
- Valsartan 40mg, 80mg and 160mg tablets and matching placebo.

Patients will be supplied with sufficient medication to last to the next visit including a small overage at visits 1, 4, 6 and 7. At each study visit where medicines are dispensed, patients will be asked to return any unused study drug and this will be returned to the pharmacy. In response to the COVID-19 pandemic re supply in person at the CRF or through home delivery at unscheduled intervals until the final MRI is performed (up to a maximum of 18 months or end of study).

Patients will be advised to take their morning study drug doses at approximately 08:00 (8 AM) and their evening dose 12 hours later at approximately 20:00 (8PM). The study medicines should be swallowed whole with water and can be taken with or without food. If a patient misses a dose of either study drug they should skip the missed dose and take the next one at the scheduled time.

Compliance will be promoted through use of tablet counts and investigators must emphasise the importance of compliance for both patient safety and study validity. If, for any reason, patients are unable to take study drug as prescribed then they will be told to contact the investigators for further advice.

6.2 Study Drug storage and supply

Investigational medicinal product (IMP) supplies will only be released to study sites by the sponsor once all the appropriate regulatory and governance approvals are in place.

All study medicines must be stored in a locked, secure area with access limited to the Investigator and authorised site staff. Study supplies should be used as directed in the study protocol and not be supplied to any persons other than study participants. Study medicines must be stored at room temperature.

6.3 Drug accountability requirements

The Investigator or designee must maintain accurate records of all study IMP movements for accountability purposes. They should include dates, quantities, batch numbers and expiry. Records must document adequately that:

- the patients were provided the doses specified by the protocol/amendment(s)
- all study drug provided was fully reconciled.

Unused study drug must not be discarded or used for any purpose other than the present study. Further information on storage requirements and supply arrangements is provided in the study specific IMP Management and Accountability Manual.

